4.1 Rationale for study design

The study is blinded for study subjects, investigators/site staff and sponsor staff until final database lock (except where indicated in Section 6.4) to reduce potential bias in the assessment of subjective readouts.

Treatment allocation is done by a stratified randomization procedure to achieve an equal distribution of disease severity among the different treatment groups.

The control group is placebo on top of standard care because there is no approved treatment to be used as active comparator for moderate to severe Sjögren's Syndrome. However, all subjects can continue with their current immunomodulatory therapy, if on a stable dose and as described in Section 6.2.1.

Two different dosing regimens (*qd* vs. *bid*) will be evaluated in CCI the study in line with the known pharmacological features (PK and PD) of LOU064 (as described in Section 4.2 and Investigator's Brochure). Commercially Confidential Information

The study treatment duration is 24 weeks, which is consistent with earlier studies conducted in this condition and is expected to allow a meaningful assessment of the safety and efficacy in SjS.

Commercially Confidential Information

4.2 Rationale for dose/regimen and duration of treatment

The highest dose planned for this study (100 mg *bid* or *qd*) has demonstrated a maximal effect for LOU064 based on predicted BTK occupancy in blood (B-cell blockade) and tissues, and inhibition of CD63 up-regulation in basophils (IB). This dose is therefore expected to provide maximum clinical effect in tissue, including lymphatic tissue for SjS. In Phase 1, doses up to 600 mg both as single and multiple doses and 200 mg as twice daily dose had been tested in human volunteers and proven to be safe (Section 5.2 in the IB).

Dose/regimen CCI

CCI the dose CCI (100 mg) is tested in a *qd* and in a *bid* regimen and compared to placebo. Due to the covalent nature of the binding of LOU064 to intracellular BTK, the duration of the treatment effect is dependent on the turn-over rate of the BTK molecule.

Commercially Confidential Information

The extent of BTK inhibition required for optimal clinical efficacy still needs to be established. However, it has been hypothesized that 70% inhibition for ~90% of each dosing period at steady state may be appropriate (Herman et al 2018) which would be exceeded clearly by both the *qd*- and *bid* regimen tested in CCI this study. Commercially Confidential Information

Commercially Confidential Information

4.3 Rationale for choice of control drug (placebo)

Comparator treatment will be placebo to provide objective evidence of potential AEs and other safety data, as well as clinical efficacy and PD data generated from subjects treated with LOU064 during the 24-week trial. Since there is no approved systemic treatment for SjS, the use of placebo is justified. Current standard-of-care for SjS patients is limited to symptomatic care for the mucosal signs and symptoms (dryness) and steroids and conventional DMARDs are often ineffective. No pharmacologic intervention is effective against the severe, disabling fatigue associated with SjS. Requirements for continuation of concomitant therapy throughout the study are described in [Section 6.2.1](#).

4.4 Purpose and timing of interim analyses/design adaptations

Commercially Confidential Information

Commercially Confidential Information

4.5 Risks and benefits

Study subjects suffering from Sjögren's Syndrome are not considered to be a specific risk population for COVID-19 infections unless caused by immunosuppressive medication. Treatment with LOU064 (remibrutinib) is expected to lead to an immunomodulatory effect with potential therapeutic consequences for the underlying immunological condition. Due to this immunomodulatory effect, a potential risk for the acquisition of infections in general cannot be excluded. This is however not considered to be specific for any viral infection including Coronavirus. It is still unclear whether the susceptibility for any viral infection during treatment with remibrutinib is increased. For established COVID-19 infections, initial reports on patients suffering from hematological malignancies and being chronically treated with a BTK-antagonist have reported relative mild disease courses (Thibaud et al 2020) and BTK-inhibitors are even considered to prevent lung injury in COVID-19 disease (Treon et al 2020). Several clinical studies have recently been initiated to test the effect of registered BTK-inhibitors on Coronavirus infections (NCT04375397, NCT04382586, NCT04380688). The most crucial measure to prevent study subjects from infection with Coronavirus is to decrease any potential exposure to the virus. Subjects with a known or suspected history of an ongoing, chronic or recurrent infectious disease (which includes Coronavirus infections) are excluded from this protocol according to Exclusion criterion #8. Based on these considerations, it is not considered that the COVID-19 pandemic changes the overall risk-benefit assessment for this study.

So far, no SjS patients have been treated with LOU064, and no reports about treatment of SjS patients with other BTK inhibitors have been published. Safety experience with LOU064 in humans is so far limited and primarily based on Phase 1 and 2 clinical studies and safety profiles from other BTK inhibitors. As of 04-Aug-2020, approximately 525 subjects (healthy volunteers and patients suffering from CSU, asthma, SjS or atopic dermatitis (AD), respectively) have been exposed to LOU064 at doses ranging from 0.5 mg to 600 mg or placebo. Administration of LOU064 did not raise any significant safety signal. A summary of AEs and pre-clinical safety data can be found in the IB.

Based on a thorough review of safety information currently available in the literature together with an assessment of safety data obtained from both clinical and preclinical experience with LOU064 as well as safety profiles from other BTK inhibitors, the following potential risks are considered for LOU064 and require close monitoring in the proposed study. When comparing the safety risks between the approved BTKi (e.g., ibrutinib and acalabrutinib) and LOU064, the relevance and importance of the study patient populations must be taken into consideration.

- **Infections:** BTK is an important signaling node downstream of cell surface receptors and expressed in several immune cells of the adaptive and innate system, including B cells, macrophages and mast cells/basophils. Therefore, LOU064 has the potential to increase the risk of infections. Patients with X-linked agammaglobulinemia (XLA) – a genetic defect associated with a lack of BTK – suffer from recurrent bacterial and enteroviral infections which may be associated with neutropenia (Kumar et al 2006). However, in XLA, BTK-deficiency leads to impaired B cell and plasma cell development and in turn to a nearly complete absence of immunoglobulins. In adult patients, BTK inhibition primarily interferes with B cell activation but not plasma cell function and is therefore not associated with a marked decrease of immunoglobulins (Hendriks et al 2014; Sun et al 2015; Nutt et al 2015). Administration of ibrutinib and acalabrutinib is associated with a risk of infection in patients suffering from B cell malignancies (Acalabrutinib SmPC 2017; Ibrutinib SmPC 2013). All patients participating in LOU064 clinical studies will be monitored closely for signs and symptoms of infections while in the study. Patients with a known history of chronic recurrent or active ongoing history of infections will be excluded from the study.
- **Impaired platelet function:** BTK is a signaling kinase in one of several platelet activation pathways. In the prescribing information for both ibrutinib and acalabrutinib, bleeding/bruising events are very common, affecting approximately 50% of patients with hematologic malignancies. Warnings on hemorrhagic events including deaths have also been described (Acalabrutinib SmPC 2017; Ibrutinib SmPC 2013). Compared to other drugs in the same class, LOU064 demonstrated a higher selectivity for BTK vs. other TEC kinases. Therefore bleeding may be less a safety concern when compared to ibrutinib and acalabrutinib because these may be more caused by inhibiting other tyrosine kinases than BTK. Patients receiving LOU064 must be closely monitored for any signs and symptoms of bleeding while in the study. Subjects with a known history of bleeding disorder and subjects taking medication that is known to increase the bleeding risk (other than acetylsalicylic acid) must be excluded from the study (see details in Section 5.2).
- **Myelomodulation:** The role of BTK inhibition in myelomodulation is not fully understood. Treatment emergent grade 3 or 4 cytopenias (neutropenia, thrombocytopenia and anaemia) were reported in patients with hematologic malignancies treated with ibrutinib and acalabrutinib (Acalabrutinib SmPC 2017; Ibrutinib SmPC 2013). Therefore, patients must be closely monitored for signs and symptoms of cytopenia while in the study, and those with a history of hematological disorders or with markedly altered hematologic parameters at baseline will be excluded from the study.

- ***Risk of cardiovascular origin:***

Commercially Confidential Information

For ibrutinib, atrial fibrillation was described for 3% to 6% of subjects across multiple trials, which might be associated with Na-channel inhibition ([Ibrutinib SmPC 2013](#)). For acalabrutinib, both atrial fibrillation and atrial flutter of any grade were reported in 3% of patients ([Acalabrutinib SmPC 2017](#)). Therefore, ECG monitoring will be implemented in this study. In addition, patients with a known history or current diagnosis of ECG abnormalities indicating a significant safety risk will be excluded from the study.

- ***Drug-drug interactions:***

Commercially Confidential Information

Please refer to the current IB (Section 5.1.5) for information on drug-drug interactions of LOU064.

- ***Reproductive toxicity:***

Commercially Confidential Information

For ibrutinib and acalabrutinib, embryofetal toxicity in animals is reported ([Acalabrutinib SmPC 2017](#); [Ibrutinib SmPC 2013](#)). Highly effective methods of contraception must be practiced for women of child-bearing potential while taking study treatment and for 7 days after stopping study medication.

Women of child-bearing potential must be informed that taking the study treatment may involve unknown risks to the fetus if pregnancy were to occur during the study, and agree that in order to participate in the study, they must adhere to the contraception requirements outlined in the exclusion criteria. If there is any question that the subject will not reliably comply, they should not enter or continue in the study.

In summary, SjS patients may benefit from treatment with LOU064 due to the effect on B-cells and autoantibodies. Additionally, this study will help improve the scientific understanding of LOU064 in the management of SjS and offer the potential of developing an innovative drug that could potentially improve the quality of life for SjS patients beyond the conventional treatment modalities currently available to them.

Potential risks are mitigated by compliance with inclusion/exclusion criteria, study procedures, close clinical monitoring and study drug discontinuation rules. As with investigational drugs in general, not all safety risks are known. Patients and investigators participating in this study will be informed should important new safety information become available.

4.5.1 Blood sample volume

A volume smaller than a typical blood donation is planned to be collected over a period of 24 weeks for the treatment period plus the 6 week screening and the 30 days follow-up period from each subject as part of the study. Additional samples may be required for safety monitoring.

Timings of blood sample collection are outlined in the assessment schedule ([Table 8-1](#)).

A summary blood log is provided in the Site Operations Manual (SOM). Instructions for all sample collection, processing, storage and shipment information is also available in the SOM and central laboratory manual.

4.6 Rationale for Public Health Emergency mitigation procedures

During a Public Health emergency as declared by Local or Regional authorities i.e., pandemic, epidemic or natural disaster, mitigation procedures to ensure participant safety and trial integrity are listed in relevant sections. Notification of the Public health emergency should be discussed with Novartis prior to implementation of mitigation procedures and permitted/approved by Local or Regional Health Authorities and Ethics Committees as appropriate.

5 Study Population

The study population will consist of adult male and female Sjögren's Syndrome (SjS) patients with ESSDAI ≥ 5 derived from 8 of 12 domains.

Commercially Confidential Information

Subjects who drop out after they have been randomized will not be replaced. CCI

5.1 Inclusion criteria

Subjects eligible for inclusion in this study have to fulfill all of the following criteria at the time of screening evaluations unless otherwise noted.

1. Signed informed consent must be obtained before any study assessment is performed.
2. Male or female patients aged 18 to 75 years
3. Classification of Sjögren's Syndrome according to the 2016 ACR/EULAR criteria ([Shiboski et al 2017](#)).
4. Screening ESSDAI (based on weighted score) ≥ 5 derived from 8 domains (biologic, hematologic, articular, cutaneous, glandular, lymphadenopathy, renal, constitutional). Subjects with involvement of one or more of the remaining 4 domains are eligible but scores of these domains will not contribute to the assessment for eligibility, but will be part of the overall ESSDAI for that subject.
5. Screening ESSPRI ≥ 5
6. Seropositive for anti-Ro/SSA antibodies at or within 3 months prior to screening
7. Unstimulated whole salivary flow rate of > 0 mL/min.
8. Able to communicate well with the Investigator to understand and comply with the requirements of the study.

5.2 Exclusion criteria

Subjects fulfilling any of the following criteria (at the time of screening evaluations unless otherwise noted) are not eligible for inclusion in this study.

1. Sjögren's Syndrome overlap syndromes where another autoimmune disease constitutes the primary illness, specifically
 - Commercially Confidential Information

- Commercially Confidential Information
- Commercially Confidential Information
- Commercially Confidential Information

2. Commercially Confidential Information

3. Rituximab or other B cell depleting drug within 12 months of Screening. For subjects who received such drug, their B cell count should be within normal range.
4. Current use of prednisone or equivalent > 15mg/d or dose change within 2 weeks prior to baseline.
5. Prior treatment with any of the following within 6 months of baseline
 - CTLA4-Fc Ig (abatacept)
 - Anti-TNF- α mAb
 - Intravenous Ig
 - Plasmapheresis
 - i.v. or oral cyclophosphamide
 - i.v. or oral cyclosporine A
6. Disease-modifying antirheumatic drugs (DMARDs) or kinase inhibitors within 3 months prior to baseline are not allowed

Commercially Confidential Information

7. Required regular use of medications known to cause, as a major side effect, dry mouth / eyes, and which have not been on a stable dose for at least 30 days prior to Screening, or any anticipated change in the treatment regimen during the course of the study.
8. HIV, Hepatitis C, Hepatitis B (HBsAg positive). If HBsAg is negative and anti-HBc positive, patient can be included if HBV-DNA is negative and patient is monitored during the study for HBsAg and HBV-DNA.
Known or suspected history of an ongoing, chronic or recurrent infectious disease including but not limited to opportunistic infections (e.g. tuberculosis, atypical mycobacterioses, listeriosis or aspergillosis).

9. History of live attenuated vaccine within 6 weeks prior to baseline or requirement to receive these vaccinations at any time during study drug treatment
10. Major surgery within 8 weeks prior to screening or surgery planned prior to end of study
11. History or current diagnosis of ECG abnormalities indicating significant risk of safety for subjects participating in the study such as:
 - Concomitant clinically significant cardiac arrhythmias, e.g. sustained ventricular tachycardia, and clinically significant second or third degree AV-block without a pacemaker
 - History of familial long QT syndrome or known family history of Torsades de Pointes
 - Resting heart rate (12 lead ECG) < 50 bpm
 - Resting QTcF \geq 450 msec (male) or \geq 460 msec (female) at pretreatment (screening) or inability to determine the QTcF interval
12. Commercially Confidential Information
13. Significant bleeding risk or coagulation disorders, including but not limited to:
Commercially Confidential Information
 - b. Requirement for anti-platelet or anticoagulant medication (for example, warfarin, or clopidogrel or Novel Oral Anti-Coagulant - NOAC) other than acetylsalicylic acid (up to 100 mg/d)
 - c. History of gastrointestinal, intracerebral or otherwise considered severe bleeding, eg in association with use of Nonsteroidal Anti-Inflammatory Drug (NSAID)
14. Commercially Confidential Information
15. Commercially Confidential Information
16. Commercially Confidential Information
17. Commercially Confidential Information
18. Screening CBC laboratory values as follows:
 - Hemoglobin levels below 10 g/dL
 - Total leukocyte count less than 3,000/ μ L
 - Platelets less than 100,000/ μ L
 - Neutrophil count \leq 1,500/ μ L
19. Commercially Confidential Information

Commercially Confidential Information

6 Treatment

6.1 Study treatment

The investigational drug will be provided by Novartis as appropriately blinded labeled bottles. CCI the bottles will contain capsules with either 50 mg active substance (LOU064) or matching Placebo.

Commercially Confidential Information

Details on the requirements for storage and management of study treatment, and instructions to be followed for subject numbering, dispensing and taking study treatment are outlined in the SOM.

6.1.1 Investigational and control drugs

Novartis Global Clinical Supply (GCS) will provide IMP supplies as detailed in the table below (Section 6.1).

Commercially Confidential Information

Supplies will be provided in a double-dummy manner.

Table 6-1 Investigational and control drug

Commercially Confidential Information				
Investigational/Control Drug	Pharmaceutical Dosage Form	Route of Administration	Supply type	Sponsor
LOU064 50 mg	Hard Gelatin Capsule	Oral	Double-blind supply	Novartis Pharma AG
LOU064 0 mg (Placebo)	Hard Gelatin Capsule	Oral	Double-blind supply	Novartis Pharma AG

Commercially Confidential Information

6.1.2 Additional study treatments

No other treatment beyond investigational drug and control drug are included in this trial.

6.1.3 Treatment arms/group

CCI subjects will be assigned on Day 1 to one of the following 3 treatment arms in a ratio of 1:1:1

- LOU064 100 mg bid
- LOU064 100 mg qd
- Placebo

Commercially Confidential Information

6.2 Other treatment(s)

6.2.1 Concomitant therapy

All medications, procedures, and significant non-drug therapies (including physical therapy and blood transfusions) administered after the subject was enrolled into the study must be recorded on the appropriate Case Report Forms.

Each concomitant drug must be individually assessed against all exclusion criteria/prohibited medication. If in doubt, the investigator should contact the Novartis medical monitor before randomizing a subject or allowing a new medication to be started. If the subject is already enrolled, contact Novartis to determine if the subject should continue participation in the study.

Commercially Confidential Information

Low-dose steroids (up to maximally 15 mg/day prednisone or equivalent) are allowed and study subjects must be on a stable dose for at least 2 weeks prior to randomization.

Concomitant treatment may include standard of care for dry eye and dry mouth symptoms, such as the use of artificial tears and artificial saliva/salivary stimulants (e.g. cevimeline, pilocarpine) at the discretion of the treating physician. Amount and frequency of use should be recorded. Please refer to [Table 6-2](#) for guidance on suggested treatment time interval prior to assessment of clinical disease outcome measurements. Artificial tears and artificial saliva are to be provided by the study center or personal physician.

Commercially Confidential Information

Table 6-2 Treatments against dryness of eyes/mouth

Treatment Type	Time interval prior outcome assessment
Artificial tears or other topical ophthalmic medications	4 hrs
Artificial saliva	4 hrs
Pilocarpine	12 hrs
Cevimeline or other salivary stimulants	24 hrs or 5x half-life whichever is longer

6.2.2 Prohibited medication

Use of treatments displayed in the below table is not allowed in study periods as indicated.

Table 6-3 Prohibited Medication

Medication	Prohibition period	Action to be taken
Use of other investigational drugs	5 half-lives or within 30 days of baseline or until pharmacodynamic effect has disappeared prior to baseline (whichever is longer) until end of study	Discontinue study treatment
Routine use of systemic corticosteroids (>15mg/d prednisone or equivalent)	14 days prior to baseline until end of study	Subject's withdrawal from the study may be required on a case-by-case basis
Rituximab or other B cell depleting drug	Within 12 months prior to screening until end of study	Subject's withdrawal from the study may be required on a case-by-case basis

Medication	Prohibition period	Action to be taken
Other immunosuppressive medication with or without known effect on SJS including but not limited to cyclosporine A, cyclophosphamide, tacrolimus, leflunomide and mycophenolate mofetil or azathioprine, hydroxychloroquine / chloroquine and methotrexate in doses above those given in Section 6.2.1 .	Within 6 months prior to baseline until end of study	Subject's withdrawal from the study may be required on a case-by-case basis
Intravenous (i.v.) immunoglobulins or plasmapheresis	Within 6 months prior to baseline until end of study	Subject's withdrawal from the study may be required on a case-by-case basis
Live attenuated vaccine	6 weeks prior to baseline until end of study	Subject's withdrawal from the study may be required on a case-by-case basis
Moderate and strong inhibitors of CYP3A4 (see Section 16.6)	From screening until end of study If LOU064 treatment is interrupted during the study to allow for transient treatment of CYP3A4 inhibitors (e.g. erythromycin) it may be resumed > 48hrs after the intermittent treatment has been stopped	Co-medication with moderate and strong CYP3A4 inhibitor is not allowed and subjects may interrupt LOU064 treatment if respective co-medication is required or cannot be replaced
Drugs which are substrates for efflux transporters P-gp and BCRP and are classified as sensitive substrates or have a narrow therapeutic index (NTI)	From screening until end of study	Co-administration may either be avoided and respective drugs (list to be provided) dosed in a staggered approach (3hrs after LOU064)
Moderate and strong inducers of CYP3A4 (see Section 16.6)	From screening until end of study	Subject's may be withdrawn from the study as the efficacy of LOU064 is compromised by concomitant use of CYP3A4 inhibitors
Any drug known to prolong QTc interval	5 half-lives or until pharmacodynamic effect has disappeared prior to baseline (whichever is longer) until end of study	Subject's withdrawal from the study may be required on a case-by-case basis
Anti-platelet or anticoagulant medication (for example, warfarin/VKAs, or clopidogrel or Novel Oral Anti-Coagulant - NOAC) other than acetylsalicylic acid (up to 100 mg/d)	From screening until end of study	Subject's withdrawal from the study may be required on a case-by-case basis

Medication	Prohibition period	Action to be taken
Newly installed DMARDs or other immune suppressive agents or changes in an existing DMARD regimen (hydroxychloroquine / chloroquine or methotrexate)	From 3 months prior to baseline until end of study	Subject's withdrawal from the study may be required on a case-by-case basis

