6.2.3 Rescue medication

There is no established, approved immunosuppressive treatment for SjS. Patients may receive nonsteroidal anti-inflammatory drugs (NSAIDs), paracetamol, or symptomatic care at the discretion of the treating physician as outlined in [Section 6.2.1](#). Each concomitant drug must be individually assessed against all exclusion criteria and prohibited medication ([Table 6-3](#)). When in doubt the investigator should contact the Novartis medical monitor before randomizing a patient or allowing a new medication to be started. If any of the medications listed in [Table 6-3](#) is deemed a necessary rescue therapy, the investigator must follow the actions to be taken outlined in this table. Any potential rescue medication is to be provided by the study center or personal physician. Patients should be encouraged to come for the end-of-study visit even when discontinued permanently from study medication.

There is no specific rescue medication for LOU064. LOU064 is eliminated within a few hours from the body and no specific antidote is necessary. Pharmacodynamic activity of LOU064 may take longer as the elimination time because of the covalent binding to the BTK-molecule. However, any direct immunosuppressive activity is not expected to take more than a few days.

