9.1 Discontinuation and completion

9.1.1 Study treatment discontinuation and study discontinuation

Discontinuation of study treatment for a subject occurs when study treatment is stopped earlier than the protocol planned duration and can be initiated by either the subject or the investigator.

The investigator must discontinue study treatment for a given subject if he/she believes that continuation would negatively impact the subject's well-being.

Study treatment must be discontinued under the following circumstances:

- Subject's decision
- Pregnancy

- Use of prohibited treatment as per recommendations in the prohibited treatment section ([Section 6.2.2](#))
- Any situation in which study participation might result in a safety risk to the subject, e.g. required surgical interventions associated with a risk of clinically significant bleeding
- Following emergency unblinding
- Emergence of the following AEs:
 - AEs including severe or serious hypersensitivity reactions for which continued exposure to the study drug would be detrimental
 - Abnormal liver laboratory results requiring discontinuation (see [Section 16.2](#))
 - Abnormal renal laboratory results requiring discontinuation (see [Section 16.3](#))
 - Platelets < 75 000/mm³
 - Any other laboratory abnormalities that in the judgment of the investigator, taking into consideration the subject's overall status, prevents the subject from continuing participation in the study
 - Patient received a live virus vaccination during the study

If discontinuation of study treatment occurs, the investigator should make a reasonable effort to understand the primary reason for the subject's premature discontinuation of study treatment and record this information.

Subjects who discontinue study treatment or who decide they do not wish to participate in the study further should NOT be considered withdrawn from the study UNLESS they withdraw their consent (see [Section 9.1.2](#)). **Where possible, they should return for the assessments** indicated in the assessment schedule ([Table 8-1](#)). If they fail to return for these assessments for unknown reasons, every effort (e.g. telephone, e-mail, letter) should be made to contact the subject/pre-designated contact as specified in the lost to follow-up section ([Section 9.1.3](#)). This contact should preferably be done according to the study visit schedule ([Table 8-1](#)).

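### Table 6-3 allows withdrawal from the study when systemic rescue is used, against Protocol 9.1.1, and so can create avoidable missing Week 24 ESSDAI values that the primary estimand calls for

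*Protocol*

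**What the plan says.** **Table 6-3 (Protocol 6.2.2).** The table has 12 rows. In eight, the action is that the subject's "withdrawal from the study may be required on a case-by-case basis". Five of these are the systemic immunomodulatory rows: corticosteroids above 15 mg/day, B-cell depletion, other immunosuppressants, intravenous immunoglobulin or plasmapheresis, and new or changed DMARDs. The other three are live vaccines, QTc-prolonging drugs, and antiplatelet or anticoagulant drugs. A ninth row, CYP3A4 inducers, says that subjects "may be withdrawn from the study as the efficacy of LOU064 is compromised". The first row (other investigational drugs) asks only that study treatment be stopped.

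**Rescue (Protocol 6.2.3).** If a drug in the table is needed as rescue, "the investigator must follow the actions to be taken outlined in this table". On later visits the section says: "Patients should be encouraged to come for the end-of-study visit even when discontinued permanently from study medication".

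**Discontinuation (Protocol 9.1.1).** The circumstances in which study treatment must be stopped include "Use of prohibited treatment as per recommendations in the prohibited treatment section" and "Patient received a live virus vaccination during the study". Subjects who stop "should NOT be considered withdrawn from the study UNLESS they withdraw their consent". The section continues: "Where possible, they should return for the assessments" in Table 8-1. The minimum data after stopping are concomitant treatments and adverse events, which may be taken by telephone or email. ESSDAI is not among them.

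**Estimand (Protocol 12.4.1; SAP 1.2.1 and 2.5.3).** The variable is Week 24 ESSDAI minus baseline. Data count regardless of early study termination, treatment interruption, or stepped-up local or systemic treatment.

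**The concern.** Table 6-3 and 9.1.1 give a site different instructions for the same event. Under 9.1.1, a patient who starts a prohibited immunosuppressant stops study drug and is still followed. Under Table 6-3, the same patient may be taken out of the study. The Protocol glossary says that no further assessments are planned after premature withdrawal, so this choice normally ends ESSDAI collection.

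That matters because an estimand that counts outcomes after rescue needs those outcomes to be measured. Where they are not, the MMRM predicts them under missing at random from the patient's earlier visits and the rest of the arm. Rescue for active disease is plausibly related to outcome, so the prediction may be wrong for just these patients. Protocol 12.4.3 provides a blinded check of the assumption and further methods if needed. SAP 2.5.5 lists no sensitivity analysis, while Protocol 12.4.4 and SAP 2.5.6 are redacted. None of these can restore a value that was not measured.

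**Working it through.** **1. Is the wording deliberate?** Table 6-3 uses both actions: stopping study treatment in its first row and withdrawal from the study in nine others. Protocol 6.6.3 (emergency unblinding) also names the two separately. The difference therefore cannot be dismissed as loose wording.

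**2. Where could a Week 24 ESSDAI come from after rescue?**

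| Patient status | Provision | Week 24 ESSDAI |
|---|---|---|
| Off drug, in study | 9.1.1 return to schedule; 8.3.1 all domains at every scheduled time point | Requested where possible; not in the minimum data |
| Withdrawn under Table 6-3 | End-of-study visit (Table 8-1, footnote 15: mandatory even after premature discontinuation) | Only if it falls in the Week 24 window |
| Withdrawn under Table 6-3 | Final evaluation at study discontinuation (9.1.2) | Only if it falls in the Week 24 window |

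Table 8-1 puts end of study on Day 199 and Week 24 on Day 169, a gap of 199 − 169 = 30 days. Protocol section 3 also describes follow-up as 30 days after the last dose. On that reading, a patient whose last dose was on Day 139 has the visit on Day 139 + 30 = Day 169, and it could count as Week 24. The SAP window rules are redacted.

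**3. Patients affected.** SAP 1.1 gives about 72 patients in three equal arms: 72/3 = 24 per arm, as stated. The documents give no rescue rate *p* and no share withdrawn *w*. Assume *p* = 0.05 to 0.20 and *w* = 0.5 to 1. Patients lost per arm = 24 × *p* × *w*:
- low: 24 × 0.05 × 0.5 = 0.6 (1.8 of 72)
- high: 24 × 0.20 × 1 = 4.8 (14.4 of 72)

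**4. Precision.** The primary contrast averages the two LOU064 arms (48 patients) against placebo (24). SE = SD × √(1/48 + 1/24) = 0.25 × SD, which is 1.0 for an assumed SD of 4 and 1.5 for an assumed SD of 6. With a fraction *f* = *p* × *w* missing in every arm and nothing recovered from earlier visits (worst case), the SE is multiplied by 1/√(1 − *f*):

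| *f* | SE ratio |
|---|---|
| 0.025 | 1.013 |
| 0.05 | 1.026 |
| 0.10 | 1.054 |
| 0.20 | 1.118 |

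**5. Bias.** Let *r* be the improvement of rescued patients beyond the missing-at-random prediction, with L for LOU064 and P for placebo. The bias in the LOU064-minus-placebo difference is *w* × (*p*L × *r*L − *p*P × *r*P); a negative value overstates the LOU064 benefit. With *r* assumed equal in the arms:
- *w* = 1, *r* = 3, *p*L = 0.05, *p*P = 0.15: 0.15 − 0.45 = −0.30 points
- rates reversed: 0.45 − 0.15 = +0.30 points
- *w* = 0.5: −0.15 and +0.15 points
- *r* = 0, or equal rates: 0

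The largest of these is 0.30/1.0 = 0.30 SE for SD 4, or 0.30/1.5 = 0.20 SE for SD 6. If rescued patients did worse than predicted (*r* negative), the signs would reverse.

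**The case against.** Section 9.1.1 cites 6.2.2 by number, says that treatment is what stops, and asks for return to the full schedule. Section 8.3.1 requires all ESSDAI domains at every scheduled time point. A reader who treats 9.1.1 as governing can reconcile the texts. This stands in part: one might infer that the protocol never asks for Week 24 ESSDAI after rescue, and that would be wrong. It is requested for anyone still in the study. But a patient withdrawn under Table 6-3 is outside that request.

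The action is also permissive, and 6.2.1 refers enrolled cases to the sponsor for a decision on continued participation. It would be wrong to infer that every rescued patient leaves the study; nothing shows how often the option would be used.

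The estimand itself lists early study termination, so the plan foresees incomplete follow-up, uses the data that exist and leaves the rest to the MMRM. That is correct, and the estimand is not made unusable. It does not explain why the protocol should add to the missing data by its own rule.

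Finally, the protocol background calls steroids and typical DMARDs largely ineffective, so *r* may be near zero for those drugs. Some rescued patients would also miss Week 24 under any wording. Both points reduce the likely harm.

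**Conclusion.** The point holds as a conflict between Table 6-3 (made binding by 6.2.3) and 9.1.1, with avoidable missing Week 24 data as its consequence. It should be corrected because the remedy is cheap and an unmeasured value cannot be recovered later.

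The size is modest and uncertain. On the assumed ranges the loss is 0.6 to 4.8 patients per arm, the SE rises by 1.3% to 11.8% at worst, and the bias lies between −0.30 and +0.30 ESSDAI points. Rescue rate, share withdrawn, rescue effect and SD are all assumptions; only the arm size comes from the documents. A reader might infer that the primary result will favour LOU064. The documents do not support that: the direction depends on which arm is rescued more and on how rescued patients fare, and the bias may be zero.

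**What to change.** 1. In the five immunomodulatory rows and the CYP3A4 inducer, QTc and anticoagulant rows of Table 6-3, write: *Discontinuation of study treatment may be required, decided case by case; the subject stays in the study and attends scheduled visits, including Week 24 ESSDAI, unless consent is withdrawn.* The argument about intensified treatment concerns the five rows; the others are included because they conflict with 9.1.1 in the same way.
2. In the live vaccine row, write: *Discontinue study treatment; the subject stays in the study and attends scheduled visits, including Week 24 ESSDAI, unless consent is withdrawn.* Section 9.1.1 already makes stopping mandatory there.
3. In 6.2.3, replace the reference to the end-of-study visit with *all remaining scheduled visits, at least Week 24 and end of study*.
4. As a supporting change, add Week 24 ESSDAI, for subjects able to attend, to the minimum data in 9.1.1. This keeps much the same qualifier as the present text, so the main gain comes from items 1 to 3.

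The cost is an amendment to nine table cells and one sentence, plus one bullet if item 4 is adopted, and a few extra visits for the few patients affected. Study drug can still be stopped for safety, consent can still be withdrawn, and the primary model does not change.
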